#### 4. TREATMENT PLAN

# 4.1 Starting Dose of Ruxolitinib and Treatment Cycle

Ruxolitinib has been developed for oral administration, a route of administration that is widely used and helps promote subject compliance to medication dosing. Both BID and QD regimens are permitted. Because of the short plasma half-life of ruxolitinib, there is little accumulation of ruxolitinib or active metabolites. The treatment period consists of multiple 28-day cycles, with subjects continuing in the study indefinitely as long as provided withdrawal criteria is not met, and there is continuing evidence of clinical benefit. Patients will continue therapy with ruxolitinib at the same dose and schedule as they have been receiving on study 2007-0169.

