## 4.4 Dosing Delays/Dose Modifications/Dose Interruptions

The course of management of the subject is at discretion of the investigator as determined in the best interest of the subject. For subjects who do not require dose interruption but have thrombocytopenia or neutropenia and no other serious safety concerns, strategy may vary case-by-case situation, to include one or more aspects of dosing schedule (ex. daily dose regimen, dosing interval, and frequency of dose or overall duration of administration of the therapy) as well as concomitant treatments to manage any untoward symptoms.

Mandatory dose decreases for safety reasons are dictated by platelet count levels. Dose modification strategies will be applied to all ongoing subjects enrolled in the study as per ruxolitinib's label (guidelines provided by FDA). When a decision is made to discontinue the subject or interrupt the therapy, then the recommendation is to consider instituting a tapering strategy based on the investigator's clinical judgment.

Utilization of a tapering strategy is based on condition of the subject, the current dosing regimen and the investigator's clinical judgment, and maintains a dose that has been shown to provide benefit to the subject or to increase the dose to a dose previously shown to provide benefit to the subject.

In any case, the following rules will ALWAYS apply:

- 1. The maximum dose must never exceed 25 mg BID, or if once-daily doses are used, dose may never exceed 100 mg QD.
- 2. Dosing must be interrupted with observation of a platelet count <25 x  $10^9$ /L.Dosing may be resumed with recovery of platelet count to a confirmed value of 35 x  $10^9$ /L or higher. Doses should be restarted at 5 mg BID, and may be increased by 5 mg BID every 2 weeks provided platelet count remains stable and exceeds 35 x  $10^9$ /L.
- 3. Dosing should be decreased by at least 5 mg BID increments with confirmed platelet count values of 25 x  $10^9/L$  to 35 x  $10^9/L$ . Dose increases may be instituted with recovery of platelets above  $50 \times 10^9/L$ .

Drug may be held up to 2 months for platelet or ANC abnormalities but if counts do not return to the level for reinstituting drug by that time, the subject will be discontinued from the study. Similarly, if drug is held for a non-hematologic toxicity for greater than two months, then the subject must be discontinued from the study.

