#### 5.4. Outside Physician Participation During Treatment

MDACC Physician communication with the outside physician is required prior to the patient returning to the local physician. This will be documented in the patient record.

A letter to the local physician outlining the patient's participation in a clinical trial will request local physician agreement to supervise the patient's care (Appendix VI).

Protocol required evaluations outside MDACC will be documented by telephone, fax or e-mail. Fax and/or e-mail will be dated and signed by the MDACC physician, indicating that they have reviewed it.

Changes in drug dose and/or schedule must be discussed with and approved by the MDACC physician investigator, or their representative prior to initiation, and will be documented in the patient record.

A copy of the informed consent, protocol abstract, treatment schema and evaluation during treatment will be provided to the local physician.

Documentation to be provided by the local physician will include drug administration records, progress notes, reports of protocol required laboratory and diagnostic studies and documentation of any hospitalizations.

The home physician will be requested to report to the MDACC physician investigator all life threatening events within 24 hours of documented occurrence.

Patients will return to MDACC every 6 cycles as long as they are enrolled in the study.

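### Minor: the single restart dose of 5 mg BID after a platelet hold (Section 4.4, rule 2) is not limited to the dose held at interruption, so a subject held at 5 mg QD could restart at twice that dose

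*Combined protocol and SAP*

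**What the plan says.** Section 4.4 opens with general latitude: "The course of management of the subject is at discretion of the investigator". It also refers to the FDA label for dose modification. It then lists numbered rules under the line "In any case, the following rules will ALWAYS apply".

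- **Rule 1** sets an absolute ceiling of 25 mg BID, or 100 mg QD for once-daily dosing.
- **Rule 2** requires interruption below 25 × 10^9/L. "Dosing may be resumed with recovery of platelet count to a confirmed value of" 35 × 10^9/L or higher. On the dose it says: "Doses should be restarted at 5 mg BID, and may be increased by 5 mg BID every 2 weeks", provided the count is stable and above 35 × 10^9/L.
- **Rule 3** covers the band above the hold level. "Dosing should be decreased by at least 5 mg BID increments with confirmed platelet count values of" 25 to 35 × 10^9/L. "Dose increases may be instituted with recovery of platelets above" 50 × 10^9/L.

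Section 4.1 states: "Both BID and QD regimens are permitted". It carries each subject's dose and schedule over from study 2007-0169 and names no minimum. Section 2.2 lists 5 mg and 25 mg tablets. For subjects followed by an outside physician, Section 5.4 adds: "Changes in drug dose and/or schedule must be discussed with and approved by the MDACC physician investigator, or their representative prior to initiation".

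**The concern.** A restart after a severe platelet fall should not exceed the dose on which the fall occurred unless someone has decided that it should. Rule 2 gives one figure for all subjects. The only dose limit in the rules is the ceiling in rule 1, which is unrelated to the individual's dose. For most dose levels 5 mg BID is a reduction. For the lowest dose that the supplied tablets allow, it is an increase.

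At that dose rules 2 and 3 also pull in opposite directions. A subject on 5 mg QD after a rule 3 reduction who stays at 25 × 10^9/L or above may have the dose raised once platelets recover above 50. If the same subject falls below 25, the worse course, rule 2 provides for double the dose at a confirmed 35. What is at stake is the platelet safety of an individual subject. The study's analyses are descriptive safety summaries, and no sample size, power or error rate depends on this rule.

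**Working it through.** The plan states the restart dose but derives no figure from it, so there is nothing to reproduce. The check is daily-dose arithmetic.

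**Inputs.** Restart dose 5 mg BID, hold below 25, resume at 35 or higher, step of 5 mg BID every 2 weeks above 35 (Section 4.4, rule 2). Ceiling (rule 1). Increase after a reduction only above 50 (rule 3). QD allowed and doses carried over (Section 4.1). Smallest tablet 5 mg (Section 2.2). Counts are × 10^9/L. The dose levels below are illustrative, because the documents do not give subjects' actual doses.

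**Step 1. Restart as a share of the held dose.** Restart = 2 × 5 = 10 mg/day. As written, ratio = 10 / held. With a cap, ratio = min(10, held) / held.

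| Held dose | mg/day | As written | With cap |
|---|---|---|---|
| 5 mg QD | 5 | 10/5 = 200% | 5/5 = 100% |
| 5 mg BID or 10 mg QD | 10 | 10/10 = 100% | 100% |
| 15 mg QD | 15 | 10/15 = 67% | 67% |
| 10 mg BID | 20 | 10/20 = 50% | 50% |
| 25 mg QD | 25 | 10/25 = 40% | 40% |
| 25 mg BID | 50 | 10/50 = 20% | 20% |
| 100 mg QD | 100 | 10/100 = 10% | 10% |

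With whole 5 mg tablets taken every day, 5 mg QD is the only dose below 10 mg/day. It is the only level at which the restart exceeds the held dose, and the only one whose restart the cap changes.

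**Step 2. Can a subject be at 5 mg QD?** The text permits it by several routes:

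- carried over from study 2007-0169;
- by investigator choice, since Section 4.4 allows dosing frequency to be changed for thrombocytopenia without interruption (5 mg BID to 5 mg QD, for example);
- by a minimum cut under rule 3: 10 − 5 = 5 mg QD if the minimum means 5 mg off the single dose, or 15 − 10 = 5 mg QD if it means 10 mg off the day.

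None of these is documented as having happened.

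**Step 3. Example path.** 10 mg QD; count 25 to 35; reduced to 5 mg QD (first reading of rule 3); count below 25, hold; confirmed 35; restart at 10 mg/day.

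**Step 4. The first increase after restart.** One step adds 2 × 5 = 10 mg/day.

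- As written, two weeks after restart: 10 + 10 = 20 mg/day. That is 20/5 = 400% of 5 mg QD and 20/10 = 200% of 5 mg BID, at a stable count above 35.
- With the cap alone, a 5 mg QD subject: 5 + 10 = 15 mg/day, or 15/5 = 300% of the held dose, at the same count. The cap therefore only postpones the excess by two weeks.
- With the cap plus a requirement of more than 50 for any increase above the held dose, that step has to wait for the level rule 3 uses. A subject held at 10 mg BID is not delayed in returning to the held dose: 10 + 10 = 20 mg/day equals it, so a count above 35 still suffices.

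**The case against.** The strongest case against is that this is an edge case with several safeguards.

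- **No affected subject is shown.** The problem exists only at 5 mg QD, the cohort is carried over from another study, and the number of subjects at that dose may be zero. This stands, and it limits the severity.
- **The text is permissive.** Resumption is *may*, the dose is *should*, the investigator has discretion, and Section 5.4 requires study-physician approval of dose changes for locally managed subjects. A reader might infer that a 5 mg QD subject would necessarily restart at double the dose. The documents do not support that; *could* is as far as they go. The safeguards do not remove the gap, because the numbered rules are said to apply in every case and an approving physician would be working from the same uncapped rule.
- **The label may already cap the restart.** Section 4.4 refers to it, but its content is not in the documents, so neither its silence nor its help can be assumed.
- **The rule 3 route depends on the reading.** If the minimum cut is 10 mg/day, 10 mg QD goes to zero and the path in Step 3 does not arise. That is true of that path, but the other routes to 5 mg QD remain.
- **A cap alone leaves the two-weekly step untouched.** This is correct, and it is why the fix has a second part.

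A reader might also infer that rule 3 needs a mandatory hold whenever its minimum cut would equal or exceed the current dose. The documents do not support that either. It would interrupt treatment at counts of 25 to 35, where the protocol reduces the dose. If the minimum were set at 10 mg/day, it would catch every subject on 5 mg BID or 10 mg QD. The two-month limit on holds could then remove subjects who are benefiting.

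**Conclusion.** The point holds as a minor defect in a written safety rule. Rule 2 has no limit tied to the held dose, and at 5 mg QD its stated restart is 200% of the dose on which platelets fell below 25 × 10^9/L. At 10 mg/day and above the restart is at or below the held dose, so the rule should not be read as unsafe in general.

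This rests on two assumptions: that 5 mg QD can occur, which the protocol permits but does not document, and that the label does not supply a cap, which cannot be checked here. There is no consequence for the study's estimates.

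**What to change.** Amend rule 2 in two respects:

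1. The restart total daily dose is the lower of 5 mg BID (10 mg/day) and the total daily dose held at interruption.
2. Later increases follow the existing two-weekly step, except that any increase taking the total daily dose above the held dose requires platelets above 50 × 10^9/L, the level rule 3 already sets for dose increases.

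The cost is amendment wording, with no added visits, tests or data items. The small downside is slower re-escalation for subjects restarted at or near their held dose, who would wait for a count above 50 rather than 35 before exceeding it. The sponsor should confirm the clinical values.

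Optionally, rule 3's minimum decrease could be stated as a total daily dose. As written, for a QD subject it can mean 5 or 10 mg/day: 5/10 = 50% or 10/10 = 100% of 10 mg QD, and 5/25 = 20% or 10/25 = 40% of 25 mg QD. This is a clarification only; no new hold should be added to rule 3.

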#### 4.5 Concomitant, Prohibited or Restricted Medications

Ruxolitinib is predominantly metabolized by CYP3A4. When administering Jakafi with strong CYP3A4 inhibitors a dose reduction is recommended. Patients should be closely monitored and the dose titrated based on safety and efficacy.

Erythropoietin or danazol may be used for patients who meet ALL of the following criteria:

- Patients with symptomatic anemia OR who are unable to maintain a Hb above 8.0 without transfusion.
- Patients for whom a dose reduction would be required to a dose < 10 mg BID OR to a dose that was previously shown to be ineffective in order to manage anemia OR patients whose current dose is sub optimally effective and cannot be dose escalated because of anemia.

Patients for whom the addition of danazol or erythropoietin is used to escalate from their current dose to gain additional efficacy may not escalate the dose of ruxolitinib until after at least 8 weeks of erythropoietin or danazol treatment and demonstration of improvement in Hb or transfusion requirements.

- Granulocyte growth factors are not allowed while study medication is being administered but may be used for severe neutropenia at the Investigator's discretion while study medication is being held.
- Anagrelide and hydroxyurea are not allowed.
- Steroid doses greater than the equivalent of 10 mg prednisone per day, unless part of a dose tapering regimen for a discontinuing subject.
- Any investigational medication other than the study medications. Use of such medications within 14 days or 6 half-lives, whichever is longer, prior to the first dose of study medication and during the study through the Follow-up Visit is prohibited.
- In emergency situations, the Investigator may use any treatment, including prohibited treatments, to manage life-threatening events including events which may be secondary to discontinuation, interruption or reduction of administration of ruxolitinib. These concomitant treatments must be documented in the subject's medical records. The treatment(s) will not be considered a protocol violation in this circumstance.
- Drugs that are classified as CYP3A4 inhibitors and/or inducers are restricted (ie: fluconazole) and should only be used with Investigator approval.

#### 4.6 Compliance:

Study medication compliance will be ascertained by tablet count of study medication at each protocol required clinic visit. Missed doses will not be considered a protocol violation unless a subject takes < 75% of the prescribed dose in a 6-month period. 6 months medication diary will be provided in every site visit.

#### **5. STUDY PROCEDURES**

#### 5.1 Cycles:

Cycles will be 28 consecutive days, on a daily or twice a day schedule. Subjects will have an every 6 cycle site visit with +/- 30 days window.

The following observations will be carried out at site study visits every 6 cycles (± 30 days):

- Targeted physical examination,
- Vital signs,
- Overall response assessment (IWG-MRT),
- EORTC QLQ-C30 questionnaire must be completed by the subject consistent with the EORTC guideline or standard guideline for completion of QOL questionnaires (see Appendix section),
- MFSAF questionnaire must be completed by the subject consistent with the standard guideline for completion of QOL questionnaires (see Appendix section)
- Blood draws for:
  - Serum chemistries (see Appendix section)
  - Hematology (CBC with differential and platelets)
- Adverse event assessment,
- Concomitant medication assessment,
- Dispense ruxolitinib, conduct study medication compliance: medication diary review, providing new one in every site visit.

Between study visits, subjects will have hematology (CBC with differential) and serum chemistry on day 1 of every 3 cycles, with +/- 14 days window (see Appendix section).

**Every 3 cycles, in between site visits,** subjects will be contacted for follow-up to assess well-being, any new or worsening signs and/or symptoms, compliance with study medication and dosing instructions, compliance with the local laboratory schedule and to answer any questions that the subject might have.

#### 5.2 End of Study or Early Termination Visit

End of Study or Early Termination visits are part of the study protocol. However, if the subject has been contacted and cannot/chooses not to return for this visit, this will not be reported as a protocol deviation. This subject decision will be documented on the CRF. Subjects must return any remaining medication to the study site for final drug reconciliation. The following procedures will be performed:

- EORTC QLQ-C30 questionnaire must be completed by the subject consistent with the EORTC guideline or standard guideline for completion of QOL questionnaires (see Appendix section).
- MFSAF questionnaire must be completed by the subject consistent with the standard guideline for completion of QOL questionnaires (see Appendix section).
- Where feasible the EORTC QLQ-C30 and MFSAF questionnaire should be administered prior to any study-specific procedures.
- Review of medical history and concomitant medication,
- Review of any adverse events,
- Complete physical examination and vital signs,
- ECOG performance status,
- Blood draws for:
  - Serum chemistries (see Appendix section)
  - Hematology (CBC with differential),
- Overall response assessment (IWG-MRT),
- A study medication tablet count will be done to assess compliance: medication diary review.

# 5.3. Duration of Participation and Number of Subjects:

Subjects may continue on therapy indefinitely if they do not meet any of the withdrawal criteria, do not have disease progression, and are receiving clinical benefit as per treating physician.

#### 5.4. Outside Physician Participation During Treatment

MDACC Physician communication with the outside physician is required prior to the patient returning to the local physician. This will be documented in the patient record.

A letter to the local physician outlining the patient's participation in a clinical trial will request local physician agreement to supervise the patient's care (Appendix VI).

Protocol required evaluations outside MDACC will be documented by telephone, fax or e-mail. Fax and/or e-mail will be dated and signed by the MDACC physician, indicating that they have reviewed it.

Changes in drug dose and/or schedule must be discussed with and approved by the MDACC physician investigator, or their representative prior to initiation, and will be documented in the patient record.

A copy of the informed consent, protocol abstract, treatment schema and evaluation during treatment will be provided to the local physician.

Documentation to be provided by the local physician will include drug administration records, progress notes, reports of protocol required laboratory and diagnostic studies and documentation of any hospitalizations.

The home physician will be requested to report to the MDACC physician investigator all life threatening events within 24 hours of documented occurrence.

Patients will return to MDACC every 6 cycles as long as they are enrolled in the study.

## 5.5 Criteria for Removal from the Study

Treatment with study drug is to be discontinued when any of the following occurs:

- Loss of therapeutic effect in the judgment of the Investigator
- Adverse event(s) that, in the judgment of the Investigator, may cause severe or permanent harm or which rule out continuation of study drug.
- Withdrawal of consent
- Lost to follow up
- Death
- Suspected pregnancy

#### 6. RESPONSE DEFINITIONS

Overall response assessment will be graded according to the International Working Group (IWG) consensus criteria for treatment response in PMF and Post-PV/ET MF:

- 1. **Complete remission (CR):** Requires all of the following in the absence of both transfusion and growth factor support:
  - i) Complete resolution of disease-related symptoms and signs including palpable hepatosplenomegaly.
  - ii) Peripheral blood count remission defined as hemoglobin > 11 g/dL, platelet count  $\geq 100 \times 10^9$ /L, and absolute neutrophil count  $\geq 1.0 \times 10^9$ /L.
  - iii) Normal leukocyte differential including disappearance of nucleated red blood cells and immature myeloid cells in the peripheral smear, in the absence of splenectomy.

- iv) Bone marrow histological remission defined as the presence of age-adjusted normocellularity, < 5% myeloblasts, and an osteomyelofibrosis grade of  $\le 1$ .
- 2. **Partial remission (PR):** Requires all of the above criteria for CR except the requirement for bone marrow histological remission. However, a repeat bone marrow biopsy is required in the assessment of PR and may or may not show favorable changes that do not however fulfill criteria for CR.
- 3. Clinical improvement (CI): Requires one of the following in the absence of both disease progression (as outlined below) and CR/PR assignment (CI response is validated only if it lasts  $for \ge 8$  weeks).
  - i) A  $\geq$  2 g/dL increase in hemoglobin level or becoming transfusion independent (applicable only for subjects with baseline hemoglobin level of < 10 g/dL).
  - ii) Either a  $\geq$  50% reduction in palpable splenomegaly of a spleen that is  $\geq$  10 cm at baseline or a spleen that is palpable at > 5 cm at baseline becomes not palpable.
  - iii) A  $\geq$  100% increase in platelet count and an absolute platelet count of  $\geq$  50,000 x  $10^9$ /L. (applicable only for subjects with baseline platelet count of < 50 x  $10^9$ /L).
  - iv) A  $\geq$  100% increase in ANC and an ANC of  $\geq$  0.5 x 10^9/L (applicable only for subjects with baseline absolute neutrophil count of < 1 x 10^9/L).
- 4. **Progressive disease:** Requires one of the following:
  - i) Progressive splenomegaly that is defined by the appearance of a previously absent splenomegaly that is palpable at > 5 cm below the left costal margin or  $a \ge 100\%$  increase in palpable distance for baseline splenomegaly of 5-10 cm or  $a \ge 50\%$  increase in palpable distance for baseline splenomegaly of > 10 cm.
  - ii) Leukemic transformation confirmed by a bone marrow blast count of  $\geq$  20%. iii) An increase in peripheral blood blast percentage to  $\geq$  20% that lasts for  $\geq$  8 weeks.
- 5. **Stable disease:** None of the above.
- 6. **Relapse:** Loss CR, PR, and CI. In other words, a patient with CR or PR is considered to have undergone relapse when he or she no longer fulfils the criteria for even CI.

#### **Footnotes**

• In patients with CR, a complete cytogenetic response is defined as failure to detect a cytogenetic abnormality in cases with a pre-existing abnormality. A partial cytogenetic response is defined as 50% or greater reduction in abnormal metaphases. In both cases, at least 20 bone marrow- or peripheral blood-derived metaphases should be analyzed.

A major molecular response is defined as the absence of a specific disease-associated mutation in peripheral blood granulocytes of previously positive cases. In the absence of a cytogenetic/molecular marker, monitoring for treatment-induced inhibition of endogenous myeloid colony formation is encouraged. Finally, baseline and post- treatment bone marrow slides are to be stained at the same time and interpreted at one sitting by a central review process.

- Transfusion dependency is defined by a history of at least 2 units of red blood cell transfusions in the last month for hemoglobin of < 8.5 g/dL that was not associated with clinically overt bleeding. Similarly, during protocol therapy, transfusions for hemoglobin of  $\geq 8.5$  g/dL is discouraged unless it is clinically indicated.
- It is acknowledged that worsening cytopenia might represent progressive disease but its inclusion as a formal criterion was avoided because of the difficulty distinguishing disease-associated from drug-induced myelosuppression. However, a decrease in hemoglobin of  $\geq 2$  g/dL, a 100% increase in transfusion requirement, and new development of transfusion dependency, each lasting for more than 3 months after the discontinuation of protocol therapy can be considered disease progression.

